8.2.5. Columbia-Suicide Severity Rating Scale

No signal of suicidal ideation and behavior has been observed in the clinical trials of guselkumab to date. However, in light of reports concerning suicidal ideation and behavior in patients with plaque psoriasis treated with an IL-17R antagonist (brodalumab) (Danesh 2016), the C-SSRS will be used as a screening tool to prospectively evaluate suicidal ideation and behavior among study participants.

The C-SSRS defines 5 subtypes of suicidal ideation and 4 possible suicidal behaviors, as well as non-suicidal self-injurious behavior and completed suicide. It will be used as a screening tool to prospectively evaluate suicidal ideation and behavior in this study, as part of a comprehensive evaluation of safety. The C-SSRS is an investigator-administered questionnaire (Mundt 2013; Posner 2011). Two versions of it will be used in this study: the ‘Baseline/Screening’ version of the C-SSRS will be conducted during the screening visit and the ‘Since Last Visit’ version of the C-SSRS will be completed at other visits as indicated in the SoA (Section 1.3).

The investigator or trained study site personnel will interview the participant and complete the C-SSRS. The C-SSRS will be provided in the local languages in accordance with local guidelines.

At screening, the C-SSRS will be the first assessment performed after signing informed consent, before any other study procedure. At all subsequent visits, the C-SSRS will be performed according to the assessment schedule and should be performed after other PROs but before any other study procedures. Participants will be interviewed by the investigator or trained study site personnel in a private, quiet place.

At the conclusion of each assessment, the trained personnel administering the C-SSRS will determine the level of suicidal ideation or behavior, if any. They will then determine the next course of action if any level of suicidal ideation or behavior is reported. The participant should not be released from the site until the C-SSRS has been reviewed by the investigator and the participant’s risk has been assessed and follow-up determined, as appropriate.

At screening (within the last 6 months) and Week I-0, participants with a C-SSRS rating of Suicidal Ideation with Intention to Act (“Ideation level 4”), Suicidal Ideation with Specific Plan and Intent (“Ideation level 5”), or suicidal behavior (actual suicide attempt, interrupted suicide attempt, aborted suicide attempt, or preparatory behaviors for making a suicide attempt), must be determined to not be at risk by the investigator based on an evaluation by a mental health professional (eg, psychiatrist, psychologist, or appropriately trained social worker or nurse) in order to be randomized.

Participants with C-SSRS ratings of Wish to be Dead (“Ideation level 1”), Non-Specific Active Suicidal Thoughts (“Ideation level 2”), Active Suicidal Ideation with Any Methods (Not Plan) without Intent to Act (“Ideation level 3”) or non-suicidal self-injurious behavior must be

determined not to be at risk by the investigator in order to be randomized in the study. Any questions regarding eligibility of such participants should be discussed with the medical monitor or designee.

For each assessment after Week I-0, the following actions should be taken, if applicable:

- No suicidal ideation or behaviors (including self-injurious behavior without suicidal intent): No further action is needed.
- Suicidal ideation levels 1-3 or non-suicidal self-injurious behavior: Participant risk is assessed by the investigator.
- Suicidal ideation levels 4 or 5 or any suicidal behavior: Participant risk assessed and referral to a mental health professional.

Interruption or the discontinuation of study intervention should be considered for any participant who reports Suicidal Ideation with Intention to Act (“Ideation level 4”), Suicidal Ideation with Specific Plan and Intent (“Ideation level 5”), or suicidal behavior (actual suicide attempt, interrupted suicide attempt, aborted suicide attempt, or preparatory behaviors for making a suicide attempt) on a postbaseline C-SSRS assessment and who is deemed to be at risk by the investigator based upon evaluation by a mental health professional. If a participant can be adequately treated with psychotherapy and/or pharmacotherapy then the participant, at the discretion of the investigator, may be continued with treatment if agreed to by the medical monitor or designee. Discussion of such participants with the medical monitor or designee is required.

Any C-SSRS finding, which in the opinion of the investigator is new or considered to be a worsening and clinically significant, should be reported on the AE eCRF (see Appendix 11 [Section 10.11], Adverse Events, Serious Adverse Events, Product Quality Complaints, and Other Safety Reporting: Definitions and Procedures for Recording, Evaluating, Follow-up, and Reporting).

8.2.6. Concomitant Medication Review

Concomitant medications will be reviewed at each visit.

8.2.7. Injection-Site Reactions

An injection-site reaction is any adverse reaction at a SC study intervention injection-site. Injection sites will be evaluated for reactions and any injection-site reaction will be recorded as an AE.

8.2.8. Hypersensitivity Reactions

Before any administration of study intervention at the study site, appropriately trained personnel and medications (eg, injectable epinephrine) must be available to treat hypersensitivity reactions, including anaphylaxis. All participants must be observed carefully for signs and symptoms of a hypersensitivity reaction (eg, urticaria, pruritis, angioedema, wheezing, dyspnea, or hypotension).

8.2.9. Adverse Events Temporally Associated with Infusion

Any AE (except laboratory abnormalities) that occurs during or within 1 hour after the IV infusion of study intervention will be carefully evaluated. Minor infusion-related AEs may be managed by slowing the rate of the IV infusion and/or treating with antihistamines and/or acetaminophen (paracetamol) as clinically indicated. If an IV infusion of study intervention is interrupted because of an AE that, in the opinion of the investigator, is not severe or does not result in a SAE, the infusion may be restarted with caution.

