7.1.1. Conditions That Require Study Intervention Discontinuation

A participant's study intervention must be discontinued under the following conditions:

1. The participant (or the participant's representative) withdraws consent to receive study intervention.
2. The investigator believes that for safety or tolerability reasons (eg, adverse event), it is in the best interest of the participant to discontinue study intervention.
3. The participant becomes pregnant or plans a pregnancy within the study period. Refer to Appendix 6 (Section 10.6), Contraceptive and Barrier Guidance and Collection of Pregnancy Information.
4. The participant initiates treatment with prohibited therapies for UC (Section 6.5.2).
5. The participant has a colectomy.
6. The participant develops an opportunistic infection.
7. The participant is deemed ineligible according to the following TB screening criteria:

A diagnosis of active TB is made.

A participant has symptoms suggestive of active TB based on follow-up assessment questions and/or physical examination or has had recent close contact with a person with active TB and cannot or will not continue to undergo additional evaluation.

A participant undergoing evaluation has a chest radiograph with evidence of current active TB and/or a positive QuantiFERON-TB[®] (or T-SPOT[®] for sites in Japan) test result (and/or a positive tuberculin skin test result in countries/territories in which the QuantiFERON-TB[®] test is not approved/registered or the tuberculin skin test is mandated by local health authorities), unless active TB can be ruled out and appropriate treatment for latent TB can be initiated prior to the next study intervention administration and continued to completion (see also Section 8.2.11 and Appendix 5 [Section 10.5]). Indeterminate QuantiFERON-TB[®] (or borderline T-SPOT[®] for sites in Japan) test results should be handled as described in Section 8.2.11. Participants with persistently indeterminate QuantiFERON-TB[®] (or borderline T-SPOT[®] for sites in Japan) test results may continue without treatment for latent TB if active TB is ruled out, their chest radiograph shows no abnormality suggestive of TB (active or old, inactive TB) and the participant has no additional risk factors for TB as determined by the investigator. This determination must be promptly reported to the medical monitor or designee and recorded in the participant's source documents and initialed by the investigator.

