Note: In Ukraine, while the QuantiFERON-TB® test is not approved/registered, it is acceptable, and an additional tuberculin skin test is not required.

A participant receiving treatment for latent TB discontinues this treatment prematurely or is noncompliant with the therapy.

8. The participant has a serious adverse reaction that is related to an injection or an infusion resulting in bronchospasm with wheezing and/or dyspnea that requires ventilatory support **OR** that results in symptomatic hypotension with a decrease in systolic blood pressure >40 mm Hg or blood pressure <90/60 mm Hg.
9. The participant has a reaction resulting in myalgia and/or arthralgia with fever and/or rash (suggestive of serum sickness and not representative of signs and symptoms of other recognized clinical syndromes) occurring 1 to 14 days after an injection of study intervention. These may be accompanied by other events including pruritus, facial/hand/lip edema, dysphagia, urticaria, sore throat, and/or headache.
10. The participant has a malignancy including squamous cell skin cancer. Consideration may be given to allowing participants who develop ≤ 2 basal cell skin cancers that are adequately treated with no evidence of residual disease to continue to receive study intervention.
11. The participant has severe liver test abnormalities that are not transient and are not explained by other etiologies, as described in Section 8.2.4 and Appendix 9 (Section 10.9; Guideline Algorithm for Monitoring, Assessment, and Evaluation of Abnormal Liver Tests in Participants With No Underlying Liver Disease). Such abnormalities would include the following:
 - ALT or AST >8 x the upper limit of normal (ULN)
 - ALT or AST >5 x ULN for more than 2 weeks
 - ALT or AST >3 x ULN **and** total bilirubin >2 x ULN **or** international normalized ratio (INR) >1.5
 - ALT or AST >3 x ULN and symptoms of hepatitis (eg, fatigue, nausea, vomiting, right upper quadrant pain or tenderness, fever, rash, and/or eosinophilia [>5%])

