7.1.2. Conditions to Consider Study Intervention Discontinuation

Discontinuation of a participant's study intervention must be strongly considered under the following conditions:

1. Persistent inadequate response or worsening of UC based on signs, symptoms, and/or laboratory values. If the participant experiences AEs consistent with clinically significant worsening of UC at any time during the study, these events should be evaluated by the investigator and the study medical monitor to decide on discontinuation of study intervention. Discontinuation of study intervention should be considered in participants with clinically significant worsening of UC where continuation of the study intervention is not in the best interest of the participant.
2. The participant develops a serious infection, including but not limited to sepsis or pneumonia.

Note: Any serious infection should be discussed with the medical monitor or designee, and study intervention should be withheld until the clinical assessment is complete.

3. The participant reports suicidal ideation with intention to act (“Ideation level 4”), suicidal ideation with specific plan and intent (“Ideation level 5”), or any suicidal behavior (interrupted suicide attempt, aborted suicide attempt, or preparatory behaviors for making a suicide attempt) on a post-baseline C-SSRS assessment. If a participant can be adequately treated with psychotherapy and/or pharmacotherapy based on an evaluation by a mental health professional, then the participant, at the discretion of the investigator, may be continued with treatment if agreed to by the medical monitor or designee. Discussion of such participants with the medical monitor or designee is required.
4. The participant develops a severe injection-site reaction or AE temporally associated with infusion.
5. Criterion deleted per Amendment 1.

If a participant discontinues study intervention for any reason before the end of the treatment period, assessments should be obtained as specified in the SoA (Section 1.3). Study intervention assigned to the participant who discontinued study intervention may not be assigned to another participant. Additional participants will not be entered.

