8.2.10. Infections

Investigators are required to evaluate participants for any signs or symptoms of infection at scheduled visits (see SoA, Section 1.3). Study intervention administration should not be given to a participant with a clinically significant, active infection. If a participant develops a serious infection, including but not limited to sepsis or pneumonia, discontinuation of study intervention must be strongly considered (Section 7.1.2). Any serious infection should be discussed with the medical monitor or designee, and study intervention should be withheld until the clinical assessment is complete.

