Note: The sponsor collects adverse events starting with the signing of the ICF (refer to All Adverse Events under Section 8.3.1, Time Period and Frequency for Collecting Adverse Events and Serious Adverse Events Information, for time of last adverse event recording).

Serious Adverse Event

A serious adverse event based on ICH and EU Guidelines on Pharmacovigilance for Medicinal Products for Human Use is any untoward medical occurrence that at any dose:

- Results in death
- Is life-threatening
(The participant was at risk of death at the time of the event. It does not refer to an event that hypothetically might have caused death if it were more severe.)
- Requires inpatient hospitalization or prolongation of existing hospitalization
- Results in persistent or significant disability/incapacity
- Is a congenital anomaly/birth defect
- Is a suspected transmission of any infectious agent via a medicinal product
- Is Medically Important*

*Medical and scientific judgment should be exercised in deciding whether expedited reporting is also appropriate in other situations, such as important medical events that may not be immediately life threatening or result in death or hospitalization but may jeopardize the participant or may require intervention to prevent one of the other outcomes listed in the definition above. These should usually be considered serious.

Unlisted (Unexpected) Adverse Event/Reference Safety Information

An adverse event is considered unlisted if the nature or severity is not consistent with the applicable product reference safety information. For guselkumab, the expectedness of an adverse event will be determined by whether or not it is listed in the Investigator's Brochure.

Adverse Event Associated With the Use of the Intervention

An adverse event is considered associated with the use of the intervention if the attribution is possible, probable, or very likely by the definitions listed below (see Attribution Definitions).

ATTRIBUTION DEFINITIONS**Not Related**

An adverse event that is not related to the use of the intervention.

Doubtful

An adverse event for which an alternative explanation is more likely, eg, concomitant treatment(s), concomitant disease(s), or the relationship in time suggests that a causal relationship is unlikely.

Possible

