An adverse event that might be due to the use of the intervention. An alternative explanation, eg, concomitant treatment(s), concomitant disease(s), is inconclusive. The relationship in time is reasonable; therefore, the causal relationship cannot be excluded.

Probable

An adverse event that might be due to the use of the intervention. The relationship in time is suggestive (eg, confirmed by dechallenge). An alternative explanation is less likely, eg, concomitant treatment(s), concomitant disease(s).

Very Likely

An adverse event that is listed as a possible adverse reaction and cannot be reasonably explained by an alternative explanation, eg, concomitant treatment(s), concomitant disease(s). The relationship in time is very suggestive (eg, it is confirmed by dechallenge and rechallenge).

SEVERITY CRITERIA

An assessment of severity grade will be made using the following general categorical descriptors:

Mild: Awareness of symptoms that are easily tolerated, causing minimal discomfort and not interfering with everyday activities.

Moderate: Sufficient discomfort is present to cause interference with normal activity.

Severe: Extreme distress, causing significant impairment of functioning or incapacitation. Prevents normal everyday activities.

The investigator should use clinical judgment in assessing the severity of events not directly experienced by the participant (eg, laboratory abnormalities).

SPECIAL REPORTING SITUATIONS

Special reporting situations must be reported by the investigator or site staff personnel to the sponsor or designee within 24 hours after being made aware of the event. Safety events of interest on a sponsor study intervention in an interventional study that may require expedited reporting or safety evaluation include, but are not limited to:

- Overdose of a sponsor study intervention
- Suspected abuse/misuse of a sponsor study intervention
- Accidental or occupational exposure to a sponsor study intervention
- Any failure of expected pharmacologic action (ie, lack of effect) of a sponsor study intervention
- Unexpected therapeutic or clinical benefit from use of a sponsor study intervention
- Medication error, intercepted medication error, or potential medication error involving a Johnson & Johnson medicinal product (with or without participant/patient exposure to the Johnson & Johnson medicinal product, eg, product name confusion, product label confusion, or intercepted prescribing or dispensing errors)

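### The infusion-restart rule in Protocol 8.2.9 joins its two safety conditions with 'or', so it permits restart after a severe or a serious reaction; it should say 'and' and point to 7.1.1 and 7.1.2

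*Protocol*

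**What the plan says.** Section 8.2.9 covers AEs that occur during an IV infusion or within the hour after it. Minor events may be handled by slowing the infusion or giving symptomatic treatment. If the infusion is interrupted for an AE that the investigator considers "is not severe or does not result in a SAE, the infusion may be restarted with caution". The section refers to no stopping rule.

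The stopping rules are in Section 7.1. In 7.1.1 the lead-in is that a participant's "study intervention must be discontinued under the following conditions". Item 8 of that list covers a serious reaction to an injection or infusion with bronchospasm needing ventilatory support, or one "that results in symptomatic hypotension with a decrease in systolic blood pressure >40 mm Hg or blood pressure <90/60 mm Hg". It sets no severity grade.

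In 7.1.2 the lead-in is weaker: discontinuation of "study intervention must be strongly considered under the following conditions". Item 4 there reads: "The participant develops a severe injection-site reaction or AE temporally associated with infusion".

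Appendix 11 (Section 10.11) defines severity and seriousness separately. Severity is graded by intensity; moderate is described as "Sufficient discomfort is present to cause interference with normal activity". Seriousness is defined by outcome and includes medically important events that "may jeopardize the participant or may require intervention to prevent one of the other outcomes listed in the definition above".

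**The concern.** The negative is repeated on both sides of 'or', so the sentence states two alternative conditions, and meeting either one unlocks the restart. To get 'neither severe nor serious', the reader has to correct the sentence. The preceding sentence on minor events suggests that this was the intent, but the operative sentence does not say it.

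This is a re-exposure rule. It is applied at the infusion visit, with the participant still in the chair, and the literal reading is the less safe one. Every induction participant is scheduled for infusions at Weeks I-0, I-4 and I-8, and Week I-12 nonresponders also receive IV study intervention at I-12, I-16 and I-20. A site working from 8.2.9 alone could restart after a reaction that 7.1.1 makes a mandatory stop. Nothing in the statistical analysis depends on the rule.

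**Working it through.** The plan gives no figure to reproduce. The check is a truth table on two attributes, followed by a comparison with the stopping rules.

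**Inputs.** S = the AE is severe (Appendix 11 severity criteria). A = the AE is an SAE (Appendix 11 definition). Rule as written in 8.2.9: restart permitted if (not S) or (not A). Corrected rule: restart permitted if (not S) and (not A).

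| Severe (S) | SAE (A) | As written: 'or' | Corrected: 'and' |
|---|---|---|---|
| No | No | Permitted | Permitted |
| No | Yes | Permitted | Not permitted |
| Yes | No | Permitted | Not permitted |
| Yes | Yes | Not permitted | Not permitted |

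As written, restart is permitted in 3 of 4 combinations; with 'and', in 1 of 4. The difference is 3 − 1 = 2 combinations: serious/non-severe and severe/non-serious. These count logical cells, not events. The cells are not equally likely, and the documents give no frequencies for them.

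**Can the two disputed combinations occur?** Yes. Severity is judged by intensity and seriousness by outcome. An event can be serious because it is medically important while graded only moderate, and an event can be severe without meeting any seriousness criterion.

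**Serious but non-severe, against 7.1.1 item 8.**
- Symptomatic hypotension with a systolic fall above 40 mm Hg or a pressure below 90/60, judged serious and graded moderate: 7.1.1 requires discontinuation, while 8.2.9 permits restart. This is a direct conflict.
- Bronchospasm needing ventilatory support: this would ordinarily be both severe and serious, so 8.2.9 already does not permit restart and there is no conflict.
- Serious reactions outside item 8, for example angioedema or wheeze managed without ventilatory support but judged medically important: item 8 does not apply. Section 8.2.8 names such signs but gives no restart rule, so 8.2.9 is the only restart instruction, and it permits restart.

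**Severe but non-serious, against 7.1.2 item 4.** That item requires only that discontinuation be strongly considered. A permission to restart is in tension with it but does not contradict it.

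**Cross-references.** Section 8.2.10 on infections, immediately after, does point to the stopping rules: for a serious infection, "discontinuation of study intervention must be strongly considered (Section 7.1.2". Section 8.2.9 has no equivalent.

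**The case against.** The strongest case against is that the protocol, read as a whole, already protects the participant. Item 2 of 7.1.1 requires discontinuation whenever the investigator believes, on safety or tolerability grounds, that stopping is in the participant's best interest. It has no severity or seriousness threshold, so it reaches both disputed combinations. Section 8.2.9 is itself permissive: the AE must be carefully evaluated, the decision rests on the investigator's opinion, and restart is optional and cautious. Where 7.1.1 says 'must', that would be expected to prevail over 'may'. Trained staff and epinephrine must be on hand, and vital signs are taken about every 30 minutes during the infusion. The site product manuals may carry their own restart rule, which cannot be seen from these documents.

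All of this lowers the risk. It does not repair the sentence: item 2 depends on the same investigator's judgment and does not withdraw a written permission pointing the other way.

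A second objection is that changing 'or' to 'and' is stricter than 7.1.2 item 4, which leaves discretion after a severe AE, and that a cross-reference alone would settle the only direct conflict. That is correct as far as it goes. A cross-reference alone would still leave restart permitted after serious reactions that item 8 does not list.

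Third, the reach is limited. The rule concerns IV induction dosing only, and Section 4.1 states that Induction Study 1 enrollment was complete before Amendment 2. This limits the practical benefit of correcting it.

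**Conclusion.** The concern holds: the sentence is wrong as written. It permits restart in 3 of 4 severity-by-seriousness combinations where 1 of 4 was almost certainly intended. The outright contradiction is confined to a serious reaction that meets the hypotension criteria of 7.1.1 item 8 and is graded below severe. The remaining excess permission covers other serious non-severe reactions and severe non-serious ones.

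The conclusion rests on the literal wording and on severity and seriousness being separate scales in Appendix 11; both are clear in the text. The intent ('neither severe nor serious') is inferred from the sentence before. The number of infusions affected cannot be estimated, because no rate of interrupted infusions by severity and seriousness is given. The point should be corrected because it sits in an operative safety instruction, but it has no bearing on power, Type I error or the efficacy analysis.

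**What to change.** In the last sentence of 8.2.9, replace the 'or' between the two negatives with 'and', and end the sentence with: subject to Sections 7.1.1 and 7.1.2. Restart is then permitted only when the AE is neither severe nor an SAE, and the stopping rules visibly take precedence.

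The cost is one sentence and no added procedures. Investigators lose the option of restarting the same infusion after a severe but non-serious AE. That is a small loss and in keeping with 7.1.2 item 4. If 'neither' was always the intent, a protocol clarification communication is enough, since Appendix 8 reserves that route for unclear text whose clarification leaves study conduct unchanged. If sites have been allowed to restart after severe or serious events, an amendment is needed.
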